APPENDIX 4. LABORATORY RELATED CTCAE SEVERITY GRADE

[figure not shown]
[figure not shown]

| AE Term | Grade 1 | Grade 2 | Grade 3 | Grade 4 | Grade 5 |
|---|---|--|--|--|----------------|
| White blood cell decreased | <LLN - 3000/mm ³ ; <LLN - 3.0 x 10 ⁹ /L | <3000 - 2000/mm ³ ; <3.0 - 2.0 x 10 ⁹ /L | <2000 - 1000/mm ³ ; <2.0 - 1.0 x 10 ⁹ /L | <1000/mm ³ ; <1.0 x 10 ⁹ /L | |
| White blood cell increased (leukocytosis) | - | - | >100,000 mm ³ | Clinical manifestations of leucostasis; urgent intervention indicated | Death |
| Anemia | Hemoglobin (Hgb) <LLN - 10.0 g/dL; <LLN - 6.2 mmol/L; <LLN - 100 g/L | Hgb <10.0 - 8.0 g/dL; <6.2 - 4.9 mmol/L; <100 - 80g/L | Hgb <8.0 g/dL; <4.9 mmol/L; <80 g/L; transfusion indicated | Life-threatening consequences; urgent intervention indicated | Death |
| Lymphocyte count decreased | <LLN - 800/mm ³ ; <LLN - 0.8 x10 ⁹ /L | <800 - 500/mm ³ ; <0.8 - 0.5 x 10 ⁹ /L | <500 - 200/mm ³ ; <0.5 - 0.2 x 10 ⁹ /L | <200/mm ³ ; <0.2 x 10 ⁹ /L | |
| Lymphocyte count increased | - | >4000 - 20,000 mm ³ | >20,000 mm ³ | - | |
| Platelet count decreased | <LLN - 75,000/mm ³ ; <LLN - 75.0 x 10 ⁹ /L | <75,000 - 50,000/mm ³ ; <75.0 - 50.0 x 10 ⁹ /L | <50,000 - 25,000/mm ³ ; <50.0 - 25.0 x 10 ⁹ /L | <25,000/mm ³ ; <25.0 x 10 ⁹ /L | |
| Serum amylase increased | >ULN - 1.5 x ULN | >1.5 - 2.0 x ULN; >2.0 - 5.0 x ULN and asymptomatic | >2.0 - 5.0 x ULN with signs or symptoms; >5.0 x ULN and asymptomatic | >5.0 x ULN and with signs or symptoms | |
| Alkaline phosphatase increased | >ULN - 2.5 x ULN if baseline was normal; 2.0 - 2.5 x baseline if baseline was abnormal | >2.5 - 5.0 x ULN if baseline was normal; >2.5 - 5.0 x baseline if baseline was abnormal | >5.0 - 20.0 x ULN if baseline was normal; >5.0 - 20.0 x baseline if baseline was abnormal | >20.0 x ULN if baseline was normal; >20.0 x baseline if baseline was abnormal | |
| Alanine aminotransferase increased | >ULN - 3.0 x ULN if baseline was normal; 1.5 - 3.0 x baseline if baseline was abnormal | >3.0 - 5.0 x ULN if baseline was normal; >3.0 - 5.0 x baseline if baseline was abnormal | >5.0 - 20.0 x ULN if baseline was normal; >5.0 - 20.0 x baseline if baseline was abnormal | >20.0 x ULN if baseline was normal; >20.0 x baseline if baseline was abnormal | |
| Aspartate aminotransferase increased | >ULN - 3.0 x ULN if baseline was normal; 1.5 - 3.0 x baseline if baseline was abnormal | >3.0 - 5.0 x ULN if baseline was normal; >3.0 - 5.0 x baseline if baseline was abnormal | >5.0 - 20.0 x ULN if baseline was normal; >5.0 - 20.0 x baseline if baseline was abnormal | >20.0 x ULN if baseline was normal; >20.0 x baseline if baseline was abnormal | |

| AE Term | Grade 1 | Grade 2 | Grade 3 | Grade 4 | Grade 5 |
|---------------------------|--|--|--|---|---------|
| Blood bilirubin increased | >ULN - 1.5 x ULN if baseline was normal; > 1.0 - 1.5 x baseline if baseline was abnormal | >1.5 - 3.0 x ULN if baseline was normal; >1.5 - 3.0 x baseline if baseline was abnormal | >3.0 - 10.0 x ULN if baseline was normal; >3.0 - 10.0 x baseline if baseline was abnormal | >10.0 x ULN if baseline was normal; >10.0 x baseline if baseline was abnormal | |
| GGT increased | >ULN - 2.5 x ULN if baseline was normal; 2.0 - 2.5 x baseline if baseline was abnormal | >2.5 - 5.0 x ULN if baseline was normal; >2.5 - 5.0 x baseline if baseline was abnormal | >5.0 - 20.0 x ULN if baseline was normal; >5.0 - 20.0 x baseline if baseline was abnormal | >20.0 x ULN if baseline was normal; >20.0 x baseline if baseline was abnormal | |
| Hemoglobin increased | Increase in >0- 2 gm/dl above ULN | Increase in >2- 4 gm/dl above ULN | Increase in >4 gm/dl above ULN | - | |
| Lipase increased | >ULN - 1.5 x ULN | >1.5 - 2.0 x ULN; >2.0 - 5.0 x ULN and asymptomatic | >2.0 - 5.0 x ULN with signs or symptoms; >5.0 x ULN and asymptomatic | >5.0 x ULN and with signs or symptoms | |
| Hypercalcemia | Corrected serum calcium of >ULN - 11.5 mg/dL; >ULN - 2.9 mmol/L; Ionized calcium >ULN - 1.5 mmol/L | Corrected serum calcium of >11.5 - 12.5 mg/dL; >2.9 - 3.1 mmol/L; Ionized calcium >1.5 - 1.6 mmol/L; symptomatic | Corrected serum calcium of >12.5 - 13.5 mg/dL; >3.1 - 3.4 mmol/L; Ionized calcium >1.6 - 1.8 mmol/L; hospitalization indicated | Corrected serum calcium of >13.5 mg/dL; >3.4 mmol/L; Ionized calcium >1.8 mmol/L; life-threatening consequences | Death |
| Hypocalcemia | Corrected serum calcium of <LLN - 8.0 mg/dL; <LLN - 2.0 mmol/L; Ionized calcium <LLN - 1.0 mmol/L | Corrected serum calcium of <8.0 - 7.0 mg/dL; <2.0 - 1.75 mmol/L; Ionized calcium <1.0 - 0.9 mmol/L; symptomatic | Corrected serum calcium of <7.0 - 6.0 mg/dL; <1.75 - 1.5 mmol/L; Ionized calcium <0.9 - 0.8 mmol/L; hospitalization indicated | Corrected serum calcium of <6.0 mg/dL; <1.5 mmol/L; Ionized calcium <0.8 mmol/L; life-threatening consequences | Death |
| Creatinine increased | >ULN - 1.5 x ULN | >1.5 - 3.0 x baseline; >1.5 - 3.0 x ULN | >3.0 x baseline; >3.0 - 6.0 x ULN | >6.0 x ULN | |
| Hyperglycemia | Abnormal glucose above baseline with no medical intervention | Change in daily management from baseline for a diabetic; oral antidiabetic agent initiated; workup for diabetes | Insulin therapy initiated; hospitalization indicated | Life-threatening consequences; urgent intervention indicated | Death |
| Hypoglycemia | <LLN - 55 mg/dL; <LLN - 3.0 mmol/L | <55 - 40 mg/dL; <3.0 - 2.2 mmol/L | <40 - 30 mg/dL; <2.2 - 1.7 mmol/L | <30 mg/dL; <1.7 mmol/L; life-threatening consequences; seizures | Death |

| AE Term | Grade 1 | Grade 2 | Grade 3 | Grade 4 | Grade 5 |
|------------------|---|--|---|--|---------|
| Hypophosphatemia | <Laboratory finding only and intervention not indicated | Oral replacement therapy indicated | Severe or medically significant but not immediately life-threatening; hospitalization or prolongation of existing hospitalization indicated | life-threatening consequences | Death |
| Hyperkalemia | >ULN - 5.5 mmol/L | >5.5 - 6.0 mmol/L; intervention initiated | >6.0 - 7.0 mmol/L; hospitalization indicated | >7.0 mmol/L; life-threatening consequences | Death |
| Hypokalemia | <LLN - 3.0 mmol/L | <LLN - 3.0 mmol/L; symptomatic; intervention indicated | <3.0 - 2.5 mmol/L; hospitalization indicated | <2.5 mmol/L; life-threatening consequences | Death |
| Hyponatremia | <LLN - 130 mmol/L | 125-129 mmol/L and asymptomatic | 125-129 mmol/L symptomatic; 120-124 mmol/L regardless of symptoms | <120 mmol/L; life-threatening consequences | Death |
| Hypernatremia | >ULN - 150 mmol/L | >150 - 155 mmol/L; intervention initiated | >155 - 160 mmol/L; hospitalization indicated | >160 mmol/L; life-threatening consequences | Death |
| Hyperuricemia | >ULN without physiologic consequences | - | >ULN with physiologic consequences | life-threatening consequences | Death |

| rNSAA | revised North Star Ambulatory Assessment total score |
| SAP | statistical analysis plan |
| SE | standard error |
| TFT | timed function test |
| UN | unstructured covariance matrix |

1. OVERVIEW

This document details the changes and the rationales for the changes in the statistical methods in analyzing Study PTC124-GD-041-DMD (hereafter referred to as Study 041) from the planned analyses for **EMA/MHRA**.

This document is prepared on the basis of the final study protocol version 4.0 (dated 21JUL2020) and the final statistical analysis plan (SAP) version 1.0 (dated 04APR2022). The reasons for the changes are described in Section 2 and the detailed list of changes are given in Section 3.

The key changes made from the final SAP are summarized below:

- The assumption of constant (linear) decline in 6MWD over 72-week underpinning the prespecified linear regression MMRM model did not hold. The observed rate of decline was found to vary over time and between visits in the 72-week study period. To accurately account for this non-linearity the ‘visit time’ variable in the MMRM model was changed from a continuous (regression) variable to a categorical variable. The assessment for linearity and adjustment of the model were conducted in accordance with EMA guidance EMEA/CHMP/295050/2013 Section 7.4.
- Although there was a clear trend in favor of ataluren’s treatment effect in the predefined primary analysis subset (modified intention-to-treat, mITT), it did not fulfill its purpose as the most sensitive subset to capture significant benefit over the finite time period of a clinical trial. Therefore, the results for the full intention-to-treat (ITT) analysis set (a pre-specified supportive population for the primary endpoint analysis) will be presented in-text. Additional sensitivity analyses were added to confirm the robustness of the conclusions from the ITT analysis set (for details see Section 3).

[figure not shown]
2. REASON FOR CHANGE FROM THE PLANNED ANALYSIS

2.1. Validity of Analysis Model Assumptions

Based on results from previous well controlled studies over 48 weeks the rate of decline in 6MWD was assumed to be constant (linear). Therefore, a linear regression MMRM model was selected as the primary analysis model for this study. As is common and good statistical practice and, in accordance with EMA guidance (EMA/CHMP/295050/2013 Section 7.4), the validity of the prespecified analysis model assumptions were checked. On assessment of the data following database lock, the linear assumption that underpinned the initial MRMM model did not hold over the 72-weeks study period in study 041.

As illustrated in [Figure 1](#) Change from Baseline in 6MWD, the rate of decline varies over time and in between study visits, see solid lines of descriptive statistics by visit. Also shown are the constant rate of change (pink and green stipulated lines) estimated from the prespecified linear regression MMRM model, these lines do not fit the descriptive statistics very well and appear to overestimate the decline for the placebo group at week 72. In order to account for the nonlinearity of the data, we then modelled the data using an MMRM that treated time on study (“visit time”) as a categorical variable instead of as originally planned a continuous variable. The MMRM with study visit as a categorical variable is a standard approach to longitudinal data where change over time is not linear and is the model prespecified in the SAP for the key secondary endpoint NSAA where nonlinearity was assumed a priori. Estimates from the MMRM model with study visit as a categorical variable fit the descriptive statistics well at all visits and appear to provide a more accurate estimate of the decline over 72 weeks. No other changes were made to the originally proposed MMRM model.

Figure 1: Line Chart of Change from Baseline of 6-minute Walk Distance (6MWD): Compare MMRM Models with Descriptive Statistics (mITT Population Double-Blind Period)

Notes: MMRM = mixed-model for repeated measures. MMRM Slope Model refers to the prespecified linear regression MMRM mode. MMRM Categorical Model refers to the MMRM model with study visit as a categorical variable.

Source: Figure 14.2.1.1.1.2

Table 1 shows the estimated mean treatment difference from descriptive statistics (arithmetic mean), the prespecified linear regression MMRM model and ANCOVA (prespecified sensitivity analysis model) as well as the modified MMRM model with study time as a categorical variable.

Table 1: Estimated Treatment Difference for Change from Baseline in 6MWD at Week 72 (mITT Population – Double-blind Period)

| Model | Estimated treatment difference (SE) (Ataluren – Placebo) | |
|--------------------------|---|---|
| | Change from Baseline at Week 72 (meters) | Average rate of change from baseline in 6MWD over 72-week double-blind period (meters/week) |
| Descriptive statistics | 8.99 | 0.12 |
| MMRM (linear regression) | 9.95 (14.9) | 0.14 (0.207) |
| ANCOVA after MI | 9.10 (13.1) | 0.13 (0.182) |
| MMRM (categorical) | 8.26 (9.1) | 0.11 (0.126) |

SE = standard error

Sources: Table 14.2.1.1.1, Table 14.2.1.1.2, Table 14.2.1.1.18, Table 14.2.1.3.1.

Although the prespecified linear regression MMRM model gives a somewhat larger estimate of treatment difference, and the modified categorical MMRM model a somewhat smaller more conservative estimate of treatment effect, the estimates from all models are quite similar and close to the descriptive statistics.

Comparing the precision (SE) of the estimates the linear regression MMRM (which utilizes all seven data points collected for each subject during the double-blind period) does not yield the expected gain in efficiency compared to the simpler ANCOVA model which utilizes only Baseline and Week 72 observations and excludes all intermittent observations. The modified MMRM model with categorical 'visit time' yields the expected gain in efficiency with the standard error of the estimates being reduced with about 30% compared to the ANCOVA model.

In conclusion, the MMRM categorial model with visits being specified as a categorical variable, and otherwise following the exact specification of the planned linear regression MMRM model, fit the data the best and provides the most conservative and precise estimate of treatment. Therefore, the linear regression MMRM model was replaced with the categorical MMRM model for all endpoints where this model was prespecified.

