9.4.5.3 North Star Ambulatory Assessment

The NSAA consists of 17 activities, each scored as 0, 1, or 2. The sum of these 17 scores will be used to form a total score. This total score will be analyzed using the ANCOVA analysis method outlined for the primary efficacy variable, for both the mITT and ITT populations, at the end of the double-blind and open-label phases. A separate analysis for the open-label phase will evaluate changes in total score in subjects with a baseline 6MWD ≥ 400 meters and < 7 years of age. Transformation of the total score to a linear scale [Mayhew 2013a] also will be performed. In addition, the odds of losing one or more of the NSAA items (score of 1 or 2 at baseline transitioning to a 0 score post-baseline) will be evaluated for ataluren versus placebo subjects using a risk ratio derived via re-sampling based analysis methods; the “lifts head” item will be excluded from this analysis because it does not fit the original construct of the NSAA based on Rasch analysis [Mayhew 2013a].

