6.1.3. Supportive/Sensitivity Analyses

6.1.3.1. Analysis of Covariance (ANCOVA) Using Multiple Imputation (MI)

As a sensitivity analysis, an ANCOVA model will be used to evaluate the difference in change in 6MWD from baseline to Week 72 after missing data have been imputed via a pattern mixture model utilizing MI. The estimated treatment difference in change from baseline of 6MWD at Week 72 and the corresponding 95% confidence interval (CI) will be provided. The ANCOVA model will include baseline concomitant corticosteroid type (deflazacort, prednisone/prednisolone), baseline 6WMD category (<300 meters, 300 to <350 meters, 350 to <400 meters, ≥ 400 meters), treatment, as well as baseline 6MWD as a covariate. For this analysis, all 6MWD will be assigned to an analysis visit according to the analysis visit window described in Section 4.8. Any subjects who lose ambulation during the study will be assigned a 6MWT result of 0 meters for the visit in which the subjects lose ambulation and for all remaining visits while they participate in the study. For subjects with missing 6MWD due to other reasons, the missing assessments at post-baseline visits will be imputed using the pattern-mixture model MI assuming the missing values are missing not at random (MNAR) utilizing the complete case missing value pattern (CCMV - subjects who completed primary efficacy assessments without missing values). Detailed imputation method is described in [Appendix 2](#).

The example SAS code is listed below:

```
PROC MIXED data=<dataset> method=reml;  
  CLASS Cortico Trt C6MWD;  
  MODEL CHG6MWD = Cortico C6MWD Trt B6MWD /CL;  
  LSMEANS TRT / pdiff CL;  
RUN;
```

where

CHG6MWD = change from baseline in 6MWD at Week 72
B6MWD = Baseline 6MWD
C6MWD = Baseline 6MWD category
Cortico = Baseline concomitant corticosteroid type
Trt = Treatment group

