6.1.3.2. ITT and PP Populations

As a supportive analysis, the primary MMRM analysis will be repeated using both the ITT and PP populations. In addition, the ANCOVA model after MI will also be repeated for ITT population. The baseline time to stand from supine (<5 seconds, ≥ 5 seconds) will be included in the testing model in the ITT analysis.

6.1.3.3. *Modification of mITT Criteria (+/- 15%)*

As supportive analyses, separate MMRM models similar to the primary analysis will be used to evaluate the change in 6MWD from baseline to Week 72 for all subjects with a baseline 6MWD ≥ 255 meters (ie, -15% from the 6MWD ≥ 300 meter lower bound) or baseline 6MWD ≥ 345 meters (ie, +15% from the 6MWD ≥ 300 meter lower bound)) and who also meet the age and stand from supine criteria for the mITT population (ie, 7 to 16 years old and time to stand from supine ≥ 5 seconds at baseline).

6.1.3.4. *Checking Missing at Random Assumption*

For the primary analysis, an additional sensitivity analysis will be employed to check the MAR assumption underlying the MMRM model where the reason for drop-out is considered. Subjects with following discontinuation reasons will be imputed using MI method using subjects in placebo arm who completed double-blind period of the study without missing values.

- Adverse event
- Withdrew consent
- Investigator decision

This analysis will be performed for mITT population. Detailed method and SAS codes are described in [Appendix 3](#).

6.1.3.5. *Using Average of Day 1 and Day 2 6MWDs Rather than Maximum*

The primary analysis uses the maximum of valid Day 1 and Day 2 6MWDs for baseline and Week 72. As a sensitivity analysis, the same analysis will be repeated with the average of valid Day 1 and Day 2 6MWDs for baseline and Week 72 for mITT population. For this analysis, the actual week for Baseline and Visit 8 will be calculated based on the first day of the visit.

6.1.3.6. *Assess the Impact of COVID19*

To assess the impact of COVID19, a sensitivity analysis will be performed similarly to the primary MMRM analysis and ANCOVA analysis after MI by removing all COVID19 impacted visits (as collected on CRF) for mITT and ITT populations. The baseline time to stand from supine (<5 seconds, ≥ 5 seconds) will be included in the testing model in the ITT analysis.

6.1.3.7. *Assess the Impact from Potential Correlation among Siblings*

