6.2.1.2. North Star Ambulatory Assessment - Total Scores

The NSAA consists of 17 activities, each scored as 0, 1, or 2. The sum of 16 scores (except for lifts head) will be used to form a total score [Mayhew 2013a]. Hereafter, this NSAA total score will be referred to as revised NSAA (rNSAA) total score. If an activity cannot be performed due to disease progression/LoA, a score of 0 will be assigned, and will not be considered as missing. If fewer than 13 of the 16 activities are performed, the total score will be considered missing. If from 13 to 16 activities are performed, the total score will be standardized by multiplying the sum of the scores in the x activities by 16/x.

The change from baseline in rNSAA total score at Week 72 based on the mITT population will be the second key secondary endpoint. An ANCOVA model will be used to evaluate the difference in change in rNSAA from baseline to Week 72 after missing data have been imputed via a pattern mixture model utilizing MI. The ANCOVA model will include factors of baseline

concomitant corticosteroid type (deflazacort, prednisone/prednisolone), baseline 6WMD category (<300 meters, 300 to <350 meters, 350 to <400 meters, \geq 400 meters), and treatment, and covariate of baseline rNSAA total score. The estimated difference in the change at Week 72 will be provided.

If both primary efficacy endpoint and the first key secondary endpoint are statistically significant at the 0.05 significance level, the rNSAA will be tested at the 0.05 (two-sided) significance level.

The same ANCOVA model will also be performed on linear transformation of the total score [Mayhew 2013a].

As a sensitivity analysis, rNSAA total score and linear score will be analyzed using a MMRM model with a random intercept. The MMRM model will include baseline concomitant corticosteroid type (deflazacort, prednisone/prednisolone), baseline 6WMD category (<300 meters, 300 to <350 meters, 350 to <400 meters, \geq 400 meters), treatment, visit (analysis visit as a categorical variable), the baseline rNSAA score as the covariate, as well as interaction of visit and treatment, and the interaction of visit and baseline rNSAA total score. The unstructured covariance matrix (UN) will be used in the MMRM model. Other types of covariance matrix (heterogenous Toeplitz, Toeplitz, and compound symmetric) will be explored in the case of non-convergence of UN.

A sample code is listed as below:

```
PROC MIXED data=<dataset> method=reml;  

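### The post-lock switch of the 6MWD model is justified by calling the categorical-visit MMRM the prespecified NSAA model, but the SAP lists it there only as a sensitivity analysis beside a deciding ANCOVA after MI

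*SAP*

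**What the plan says.** The change document, section 2.1, reports that the linear trend behind the planned 6MWD model was checked after database lock and found not to hold. It adopts an MMRM with visit as a category and says that this "is the model prespecified in the SAP for the key secondary endpoint NSAA where nonlinearity was assumed a priori".

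The double-blind SAP, section 6.2.1.2, gives two analyses of rNSAA. The one tied to the fixed-sequence test is "An ANCOVA model will be used to evaluate the difference in change in rNSAA from baseline to Week 72 after missing data have been imputed". The MMRM comes later: "As a sensitivity analysis, rNSAA total score and linear score will be analyzed using a MMRM model with a random intercept". Its terms include "visit (analysis visit as a categorical variable"), so it is the model that the change document has in mind. The protocol, section 9.4.5.3, names only ANCOVA for NSAA: "This total score will be analyzed using the ANCOVA analysis method outlined for the primary efficacy variable".

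For 6MWD, section 6.1.3.1 of the double-blind SAP plans, as a sensitivity analysis, that "an ANCOVA model will be used to evaluate the difference in change in 6MWD from baseline to Week 72 after missing data have been imputed". Section 6.1.3.2 adds that "the ANCOVA model after MI will also be repeated for ITT population".

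Later in the change document, section 3.2.1 makes the categorical MMRM the lead model for the key secondary endpoints, rNSAA included. Section 3.2.1.2 states that the planned rNSAA analyses are unchanged and lists both ANCOVA after MI and the categorical MMRM.

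**The concern.** The 6MWD model was replaced after lock, with estimates by treatment arm in hand. A claim that the replacement already had prespecified standing on a sister endpoint therefore carries weight: it suggests that the sponsor had settled on this model for non-linear decline before seeing data. If the SAP gave the model only a supporting role, and gave no non-linearity reason for it, that reassurance is not available.

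Two further things are at stake. First, the deciding analysis of rNSAA may shift from ANCOVA to the MMRM without being recorded as a change. Second, the SAP already held a Week 72 analysis of 6MWD that does not rely on a linear trend. A reader should be able to compare it with the chosen model on equal terms, because the chosen model gives the narrower interval.

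**Working it through.** **Status of the categorical MMRM**

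| Place | rNSAA deciding analysis | Role of categorical MMRM |
|---|---|---|
| Protocol 9.4.5.3 | ANCOVA | not mentioned |
| Double-blind SAP 6.2.1.2 | ANCOVA after MI, Week 72, mITT | sensitivity analysis |
| Change document 2.1 | not stated | the prespecified model for NSAA |
| Change document 3.2.1 | categorical MMRM, ITT | lead model |
| Change document 3.2.1.2 | said to be unchanged | listed with ANCOVA after MI |
| Open-label SAP 6.2.3 | ANCOVA after MI, Week 144, ITT | not mentioned |

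The third and fourth rows do not agree with the second. The fourth and fifth do not agree with each other. I found no statement in the protocol or the SAPs that NSAA was expected to change non-linearly over time.

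**Size for 6MWD in mITT**

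Inputs are the Week 72 differences and standard errors in Table 1 of the change document, section 2.1.

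1. The document's own figure. It reports that the standard error falls by about 30% from ANCOVA to the categorical MMRM: 1 - 9.1/13.1 = 30.5% (29.9% to 31.2% allowing for rounding). This reproduces.
2. The per-week column is the Week 72 column divided by 72. For example, 9.10/72 = 0.126 with SE 13.1/72 = 0.182, and 8.26/72 = 0.115 with SE 9.1/72 = 0.126. These agree with the table within rounding.
3. Intervals by the normal approximation, estimate ± 1.96 × SE, with z = estimate/SE:

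| Model | Difference (SE), m | 95% CI, m | z | two-sided p |
|---|---|---|---|---|
| Linear MMRM (planned primary) | 9.95 (14.9) | -19.3 to 39.2 | 0.67 | 0.50 |
| ANCOVA after MI (planned sensitivity) | 9.10 (13.1) | -16.6 to 34.8 | 0.69 | 0.49 |
| Categorical MMRM (adopted after lock) | 8.26 (9.1) | -9.6 to 26.1 | 0.91 | 0.36 |

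4. Relative width: 13.1/9.1 = 1.44 (1.43 to 1.45 with rounding), so the ANCOVA interval is 44% wider.
5. Smallest difference that would reach p < 0.05: 1.96 × 13.1 = 25.7 m with ANCOVA, and 1.96 × 9.1 = 17.8 m with the categorical MMRM.

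The change document calls the categorical model the most conservative. That is true of its point estimate, but its z value is the largest of the three.

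**The case against.** The strongest reply is that the sentence in section 2.1 is literally defensible. The categorical MMRM is in the SAP for rNSAA, with its terms, covariance structures and sample code, and a prespecified sensitivity analysis is still prespecified. A reader might infer that no SAP precedent exists at all; the documents do not support that. What remains is that the sentence calls it the model prespecified for that endpoint, omits its sensitivity role, and adds a reason that the SAP does not give. The sample code in 6.2.1.2 carries 6MWD variable names, but the text introducing it concerns rNSAA, and the double-blind SAP plans no categorical-visit model for 6MWD.

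A reader might also infer that the SAP required ANCOVA once linearity failed. It does not. It has no fallback rule, it consistently calls ANCOVA after MI a sensitivity analysis, and section 6.1.3.8 also plans a stratified Wilcoxon test in mITT that needs no linear trend. Section 4.10 ranks ANCOVA second because it relies on nearly all visits being in window. That reason does not favour the categorical MMRM, which also replaces actual week with analysis visit.

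The two models are not interchangeable either. The planned primary model assumes MAR, while ANCOVA after MI assumes MNAR with complete-case (CCMV) imputation. Making ANCOVA the sole lead result would change the missing-data assumption too, so it is a trade-off and not a plain correction. For the same reason the gap in standard errors cannot be put down to the handling of time alone.

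Finally, the change document is open about much of this. It dates the check to after lock, calls the new model modified, and prints both results side by side. That stands, but it does not repair the statement about NSAA.

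**Conclusion.** The concern holds in a limited form. The change document overstates the prespecified standing of the categorical MMRM for NSAA and offers an advance assumption of non-linearity that the available text does not contain. Its sections 3.2.1 and 3.2.1.2 cannot both be right about rNSAA when read against section 6.2.1.2 of the double-blind SAP.

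For 6MWD in mITT, the planned Week 72 ANCOVA has an interval 44% wider than the adopted model. It would be tempting to infer that the switch turned a negative result into a positive one. The documents do not show that: all three mITT intervals include zero, and the adopted model has the smallest estimate. No ITT estimates or standard errors are given, so the effect on the re-designated ITT analysis cannot be computed.

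The intervals assume approximate normality and the rounded figures in Table 1. The finding that no a priori statement exists is limited to the public text, in which the protocol's section on the primary efficacy analysis does not appear. The categorical MMRM is a legitimate method; the problem is the status claimed for it.

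**What to change.** 1. In section 2.1 of the change document, say that the categorical-visit MMRM was a sensitivity analysis for rNSAA and that ANCOVA after MI was the deciding one. Delete the statement that non-linearity was assumed in advance, or give its source.
2. Reconcile sections 3.2.1 and 3.2.1.2 with section 6.2.1.2 of the double-blind SAP, so that ANCOVA after MI stays the deciding rNSAA analysis.
3. Label the categorical MMRM for 6MWD as post hoc and chosen after database lock. Report the planned ANCOVA after MI beside it in-text for both mITT and ITT, and note that it assumes MNAR with CCMV imputation where the MMRM assumes MAR.

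Both 6MWD analyses are already planned for ITT and already run for mITT, so the cost is wording and table layout. The downside for the sponsor is that the reported evidence will look less precise.
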